1. CCI
 - 2.
- 

A schematic of the study design is included as [Figure 6.a](#). A schedule of assessments is listed in the protocol, [Appendix A](#).

Figure 6.a Schematic of Study Design

* Non-Hispanic/Latino Caucasian, Hispanic/Latino Caucasian, and non-Caucasian subjects alike will be stratified into high- and low-risk strata using the same biomarker risk algorithm; however, target sample size for primary endpoint analyses refers to non-Hispanic/Latino Caucasian subjects only.

** As this is an event-driven study, double-blind treatment duration will depend on the time it takes for a total of 202 conversions from cognitively normal status to MCI due to AD dementia to occur in the high-risk non-Hispanic/Latino Caucasian population; conversions from cognitively normal status to AD will also be included in this total. Study visits to the testing center will take place every 6 months after the Randomization Visit.

7.0 ANALYSIS ENDPOINTS

7.1 Primary Endpoints

For biomarker risk algorithm qualification:

Time to diagnosis of MCI due to AD for placebo-treated, high-risk, non-Hispanic/Latino Caucasian subjects versus placebo-treated, low-risk, non-Hispanic/Latino Caucasian subjects.

For efficacy evaluation of pioglitazone:

Time to diagnosis of MCI due to AD for pioglitazone-treated, non-Hispanic/Latino Caucasian subjects versus placebo-treated non-Hispanic/Latino, Caucasian subjects in the high-risk stratum.

7.2 Key Secondary Endpoints

- Change from baseline to Year 4 for cognitive decline on composite score on the cognitive battery for pioglitazone-treated subjects versus placebo-treated subjects in the high-risk stratum.
- Changes from baseline to Year 4 in instrumental activities of daily living (Alzheimer's Disease Cooperative Study Activities of Daily Living - Prevention Instrument [ADCS ADL-PI]) between pioglitazone-treated and placebo-treated groups of the high-risk stratum.

7.2.1 Additional Endpoints

7.2.1.1 Safety Assessments

- Safety and tolerability: adverse events (including adverse events of special interest), vital signs, body weight, electrocardiogram (ECG), clinical laboratory data, and physical exam findings.

7.2.1.2 Additional Endpoints

- Change from baseline to all scheduled visits where the following is assessed (6-month visits and End-of-Study (EoS) / Early Withdrawal (EW)): cognitive decline on composite score on the cognitive battery for pioglitazone-treated subjects versus placebo-treated subjects in the high-risk stratum.

Change from baseline to all scheduled visits where the following is assessed (6-month visits and End-of-Study (EoS) / Early Withdrawal (EW)): cognitive decline on tests and domain scores within the cognitive battery (see [Table 9.b](#)) for pioglitazone-treated subjects versus placebo-treated subjects in the high-risk stratum.

- Changes from baseline to all scheduled visits where the following is assessed (6-month visits and EoS/EW): instrumental activities of daily living (Alzheimer's Disease Cooperative Study Activities of Daily Living - Prevention Instrument [ADCS ADL-PI]) between pioglitazone-treated and placebo-treated groups of the high-risk stratum.

CCI

-
-
-
-
-
-
-
-
-
-
-
-
-
-
-

- CCI 

Although change-from-baseline endpoints will be assessed at all visits, the primary time frame for purposes of efficacy analysis is the change from baseline to Month 48 (Year 4).

8.0 DETERMINATION OF SAMPLE SIZE

Background Information for Determining Sample Sizes

Using 73 years as the age at entry (+5 years = age 78), a conversion rate of around 18% over 5 years can be expected (see [Table 8.a](#)). This is based on:

- The TOMM40 rs10524523 allele frequencies from the Duke Alzheimer’s Disease Research Center (ADRC), Cache County, and Wisconsin cohorts.
- The assessment of peer-reviewed published incident MCI in normal individuals.
- The effect of APOE on the incidence of AD.

Table 8.a Conversion Rate Estimates Based on Analysis of 3 Cohorts, Cognitive Impairment Incidence, and Observed TOMM40 rs10524523 Allele Frequencies

TOMM40 rs10524523 Genotype	Duke Bryan ADRC Frequency	Wisconsin Frequency	Cache Frequency	Cohort Total Count	Age 78 (Proportion Converted)	
					Proportion	Number of Converted Subjects
L/L	0.05	0.04	0.02	189	0.53	100
VL/L	0.14	0.15	0.13	543	0.34	185
S/L	0.17	0.20	0.14	669	0.22	147
S/S	0.23	0.16	0.17	929	0.14	130
S/VL	0.31	0.31	0.36	1236	0.10	124
VL/VL	0.11	0.14	0.18	433	0.05	22
Total count = 3999					Total converted	708
					Overall conversion rate	0.177

Taking into account the age ranges that will be enrolled in the phase 3 study, a 5-year conversion rate of 15% will be assumed for non-Hispanic/Latino Caucasian placebo subjects within the high-risk stratum identified by the enrichment process. Based on the expected 5-year conversion rate of 15%, the time-to-event was modeled using an exponential mathematical model for planning the study sample size.

Similarly, a 5-year conversion rate of 4% will be assumed for non-Hispanic/Latino Caucasian placebo subjects within the low-risk stratum. Thus, it is important to recognize that this summary of the data demonstrates nearly a four-fold enrichment of events over the population rate using the risk algorithm.

Determination of Sample Size for the Phase 3 Study Based on the High-Risk Stratum

The sample size for this study is based on the event-driven analysis that is planned for comparing treatment groups within the high-risk stratum. For the purposes of this study, it is assumed that the placebo-treated non-Hispanic/Latino Caucasian subjects in the high-risk stratum will have an event rate of 15% over a 5-year period. This is more conservative than the 18% cited in the table, to assure adequate sample size. With a clinically meaningful improvement of a reduction in event rate of at least 40%, the target event rate for the active treatment group will be 9% over 5 years. Furthermore, the following specifications are used: $\alpha=0.01$, a 2-sided statistical test based on survival analysis, power=90%, annual dropout rate of 12% (or cumulative dropout rate of 47% over 5 years). In order to detect a difference of the specified magnitude ($\geq 40\%$ reduction in conversion rates over 5 years), at least 202 events must be observed during the course of the study in non-Hispanic/Latino Caucasian subjects (primary efficacy analysis). Based on these assumptions and the fact that only non-Hispanic/Latino Caucasian subjects will be used for the primary analyses, a total of 2,346 non-Hispanic/Latino Caucasian subjects (1,173 on pioglitazone/1,173 on placebo) should be enrolled from the high-risk stratum for randomization.

Sample Size for the Phase 3 Study Based On Qualifying the Test Used to Stratify Subjects

While using data from the results of risk stratification and not a comparison between randomized groups, the same analysis as specified for comparing the treatment groups within the high-risk stratum will also be used to compare the two placebo groups (high-risk placebo and low-risk placebo). Thus, assuming that the placebo-treated subjects in the low-risk stratum will have a conversion rate of 4% over a 5-year follow-up period, then approximately 314 non-Hispanic/Latino Caucasian subjects identified as low-risk for the event should be enrolled in that stratum. This number of subjects enrolled in the low-risk stratum will provide very high power (99% with $\alpha=0.01$) to validate the enrichment algorithm with the assumed 5-year conversion rates (ie, 15% vs. 4%).

Sample Size for the vMRI Substudy

This substudy is not designed or powered to assess any quantitative changes in the brain. Based on clinical judgment, a sample size of 300 subjects is believed to be sufficient to evaluate possible qualitative changes in the brain via vMRI.

9.0 METHODS OF ANALYSIS AND PRESENTATION

9.1 General Considerations

9.1.1 Statistical Software

All statistical analyses will be performed using SAS[®] Version 9.1.3 or higher.

9.1.2 Summary Statistics and Precision

All tabulations of analysis results will include summaries for all three treatment groups: high-risk placebo, high-risk pioglitazone, and low-risk placebo.

Except when noted as otherwise, all confidence intervals (CIs), statistical tests, and resulting p-values will be reported as nominal 2-sided and will be assessed at the 5% significance level. No adjustments will be made for multiplicity except for primary efficacy and key secondary endpoints.

For continuous variables, descriptive statistics will include the number of subjects (n), mean, standard deviation (SD) or standard error (SE) as appropriate, minimum, median, and maximum. The number of decimal places displayed for each statistic will be determined as follows:

- Mean and median: 1 more than the number of reported decimal places. (For electronic case report form (eCRF) data, the number of reported decimal places will be equal to the number of decimal places allotted in the eCRF.)
- SD and SE: 2 more than the number of reported decimal places allotted in the eCRF.
- Minimum and maximum: equal to the number of reported decimal places allotted in the eCRF.
- Confidence intervals will be presented using the same number of reported decimal places as the parameters (eg, mean).

For categorical data, frequency counts and percentages will be presented. Percentages will be reported to 1 decimal place.

The data summaries will be accompanied by individual subject data listings sorted by treatment (including low-risk placebo), study center and subject identifier. All data available from eCRFs will be listed. The actual day relative to the start of treatment will be determined and included in the listings.

Derived analysis datasets will be produced from SDTM data and laboratory data. This allows for convenient reviewing of the data as well as any necessary supplemental analyses. All data from the raw datasets will be included in the derived datasets. Derived dataset specifications will be developed to include the names and definitions of derived variables in the derived SAS datasets.

9.1.3 Definition of Study Day and Study Visit Windows

A windowing convention will be used to determine the analysis value for a given study visit that applies to observed data.

Study Day -1 corresponds to the randomization date. Other study days are defined relative to Study Day 1, the date of first double-blind study drug dose. Relative day is calculated as (date of interest - date of first dose +1) for study days on or after the date of first dose and as (date of interest - date of first dose) for study days prior to the first dose date.

For each visit, a window will be defined such that the lower and upper bounds of each window is generally the midpoint between 2 consecutive study visits. The visit windows and applicable study day ranges are presented below in [Table 9.a](#).

Table 9.a Visit Windows

Nominal Visit Month	Nominal Visit Day	vMRI	Height, ECG, Chemistry and Hematology, PK, RU, DNA/RNA, PE	All Other Variables (c)
Baseline	-36 to -1 (a)	≤ -1	≤ -1 (b)	≤ -1
6	183			2—273
12	365		2—547	274—456
18	548			457—638
24	731	639—821	548—912	639—821
30	913			822—1003
36	1096		913—1277	1004—1186
42	1278			1187—1369
48	1461		1278—1643	1370—1551
54	1644			1552—1734
60	1826		1644—1917	1735—1917
66/Final (d)	2009	≥1370	≥1918	≥1918

(a) Consistent with SDTM dataset standards, date of first dose of double-blind study drug is defined as Day 1, and the day before is defined as Day -1. Per the protocol, date of first dose of dose of double-blind study drug is scheduled for the day after randomization. Exemptions were granted on a case-by-case basis for subjects who had a screening-to-randomization time frame greater than the 35-day window planned per the protocol.

(b) No baseline assessment for PK samples.

(c) CDR and NPI-Q are collected only at Baseline (Visit 2), unscheduled visits (eg, comprehensive medical follow-up visits) and End of Study / Early Withdrawal.

(d) The planned study duration of 5.5 years is approximate, since this is an event-driven trial.

For safety variables, visit windows are exhaustive and the lower and upper bounds of each window are the midpoints between the scheduled visit days for the current visit and the adjacent visits.

More than 1 result for a parameter may be obtained in a visit window. In such an event, the result with the date closest to the scheduled visit day will be used. In the event of 2 observations equidistant to the scheduled visit day, the later of the observations will be used.

In general, the baseline value for a variable is defined as the last observation prior to the first dose of double-blind study medication (visit date \leq first dose date), including the screening value, if necessary.

Adverse events that start more than 30 days after the last dose of double-blind study medication (start date – last dose date >30) will be listed, but excluded from the summaries and analyses. For efficacy and other safety data, data that are obtained more than 7 days after the last dose of double-blind study medication (visit date – last dose date > 7) will be listed, but excluded from summaries and analyses. (Note: This efficacy data window only applies to determining which data are included/excluded from the summary statistics and formal statistical analysis tables for a given efficacy endpoint. All events of MCI due to AD (or AD dementia) as determined by the adjudication committee will be included in the time-to-event analyses, without regard to the date of last dose of double-blind study medication.)

If the date of first dose of double-blind study drug collected in the eCRF is missing, then for summary purposes the day after the first dispense date will be used as an estimate for the date of first dose. However, if all dispensed study drug is returned, then the subject is assumed to have not taken any study drug, and the first dose date will not be imputed.

If the date of last double-blind study drug dose collected in the eCRF is missing, then the earliest of the following dates will be used for the last dose date for analysis and summary purposes: date of death, date of last visit (recorded in the eCRF), last double-blind study drug return date, and the last double-blind study drug dispense date (following the last drug return date) + 200 days (ie, the double-blind study drug dispensing interval corresponding to the number of study drug tablets dispensed).

The study window convention will not be applied to the eCRF data listings. The data listings for eCRF data will display the raw data as collected and entered in the eCRF. For efficacy listings, windowed visits will also be shown on the listings.

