Appendix G Corrections to the MMSE based on Education and Age

At the Screening Visit, the MMSE should be adjusted at the site by the following:

- Low Education Strata: +1

Country	Low Education (in years)
Australia	0-9
Germany	0-11
Switzerland	0-11
U.K.	0-10
U.S.	0-11

- Old Age (76-83): +1

Appendix H A Sub Study To Evaluate the Effects of Pioglitazone on Whole and Regional Brain Volume over Time

Study Title

Assessment of pioglitazone effects on whole and regional brain volume in a sub-population of cognitively normal elderly subjects enrolled in a double blind, randomized, placebo controlled, parallel group study to simultaneously qualify a biomarker algorithm for prognosis of risk of developing mild cognitive impairment due to Alzheimer's disease (MCI due to AD) and to test the safety and efficacy of pioglitazone (AD-4833 SR 0.8 mg QD) to delay the onset of MCI due to AD in cognitively normal subjects.

Study Design

In addition to their participation in the main phase 3 study, approximately 300 cognitively normal elderly subjects will participate in a sub study at selected sites. Subjects will sign a separate informed consent form (ICF) in order to participate in this sub-study. Subjects who fulfill all inclusion criterion and none of the exclusion criteria for the sub-study will be selected in a double-blind fashion to represent a 5:4 randomization ratio between pioglitazone and placebo assignment. Subjects in this sub-study will be scanned to assess brain volume (vMRI). Serial brain MRI scans will be performed at baseline, 2 years, and EoS/EW (3 timepoints in total). If an MRI scan has been performed for the main study or the sub study within 6 months of a required timepoint, a separate MRI scan does not need to be performed.

Schedule of Additional Study Procedures for the Sub-Study

	Screening Visit 1	Baseline Visit 2	Randomization Visit 3	Double-Blind Treatment	EoS/EW Visit
Study Month:	-4	-1	0 (Day 0)	24	
Visit Window:	Max Day -125	Max Day -35		±2 weeks	
Informed consent (a)	X	X			
Incl/Excl Criteria	X	X	X		
vMRI scan (Brain Volume)		X		X (b)	X (b)

(a) All subjects should sign a separate informed consent to participate in the sub-study at either visit 1 or visit 2, must occur prior to any sub-study procedures taking place.

(b) This assessment only needs to be administered at this visit if it occurs greater than 6 months from the last administration for either the main study or the sub study.

Duration of Treatment

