The total duration of the vMRI sub study will be the same duration as the main study.

Primary Objective

1. To evaluate changes in brain volume in subjects receiving pioglitazone versus subjects receiving placebo.

CONFIDENTIAL

Primary Endpoint

1. Changes from baseline in vMRI in whole brain and specific brain regions of interest at 2 years and EoS/EW (in subjects enrolled in the sub study).

Inclusion / Exclusion Criterion

All inclusion/exclusion criteria specified in the main study will also apply to the sub-study. An additional exclusion criterion to the main study for the sub study is as follows:

1. Subject has a contraindication to having MRI, for example because of ferromagnetic foreign bodies (eg, unremovable ferromagnetic dental work), medical devices such as aneurysm clips or cardiac pacemakers, or lead-based tattoos.

Sample Size

This substudy is not designed or powered to assess any quantitative changes in the brain. Based on clinical judgment, a sample size of 300 subjects is believed to be sufficient to evaluate possible qualitative changes in the brain via vMRI.

IVRS/IWRS will be utilized to randomize subjects into this sub study in order to provide balance between high risk placebo and high risk pioglitazone.

MRI protocol minimum standards

All MRI scans will be reviewed centrally at a designated imaging lab. All MRI scans will also be reviewed at the local labs for safety.

Brain volumetric measurements will be done using T1-weighted MRI. Specific MRI parameters to be used in this study along with further instructions about the imaging will be detailed in the imaging procedure manual.

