In the above model, baseline is the baseline value and Change is the change from baseline value.

Volumetric MRI (vMRI) variables were collected in a substudy of approximately 300 subjects. These volumetric MRI atrophy and enlargement endpoints are calculated with sophisticated algorithms that derive the change in the brain by registering each of the follow-up time points against the baseline and calculating algorithmically the change (ie, this is not determined by calculating the volume at baseline and then independently calculating the volume at a given post-baseline visit and then subtracting). The vMRI variables left hippocampal atrophy, right hippocampal atrophy, whole brain atrophy, and ventricular enlargement will each be analyzed as continuous variables by study visit using ANCOVA models similar to the ones described above for the NPI-Q variables. The appropriate baseline variable (ie, left hippocampal volume, right hippocampal volume, whole brain volume, or ventricular volume), as well as intracranial volume, will be used as covariates in each of these models.

For each efficacy variable for which MMRM analysis of covariance analyses will be done, summary statistics (n, mean, SD, median, minimum, and maximum) by treatment group (including low-risk placebo) will be given for the actual values and change-from-baseline values for each visit and EoS/EW.

For the single-item variables MMSE_i, GDS_i, ADCS_i, EQ5D_i, SF36_i, IQ_i, ADLQ_i, and NPIQ_i, the counts and percentages of each possible value will be tabulated by treatment group (including low-risk placebo) for each visit and EoS/EW. For single-item variables which have a meaningful numerical score, summary statistics (n, mean, SD, median, minimum, and maximum) by treatment group (including low-risk placebo) will be given for the actual values and change-from-baseline values for each visit and EoS/EW.

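### SAP Table 9.a gives follow-up vMRI scans only two analysis windows (days 639-821 and day 1370 onward), so early-withdrawal scans on other days, for up to about a quarter of sub-study subjects, have no assigned visit

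*SAP*

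**What the plan says.** Protocol Appendix H defines the sub-study endpoint as "Changes from baseline in vMRI in whole brain and specific brain regions of interest at 2 years and EoS/EW", on this schedule: "Serial brain MRI scans will be performed at baseline, 2 years, and EoS/EW (3 timepoints in total". Footnote (b) to its schedule, which applies to both the Month 24 and the EoS/EW scan, limits when a scan is needed: "This assessment only needs to be administered at this visit if it occurs greater than 6 months from the last administration". The Study Design text of the appendix says the same from the other side: "If an MRI scan has been performed for the main study or the sub study within 6 months of a required timepoint", no separate scan is required.

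SAP 9.1.3 states the windowing rule, that "the lower and upper bounds of each window is generally the midpoint between 2 consecutive study visits", and Table 9.a applies it. The vMRI column has three entries: baseline (day -1 or earlier), Month 24 (nominal day 731, days 639-821) and 66/Final (nominal day 2009, day 1370 or later). The table's other two columns run without a break from day 2. Full coverage is claimed only in part: "For safety variables, visit windows are exhaustive".

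SAP 9.9.9 says that the vMRI variables "will each be analyzed as continuous variables by study visit using ANCOVA models" similar to those used for NPI-Q.

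**The concern.** An early-withdrawal scan can fall on any study day, but the table gives follow-up vMRI scans a home only near 2 years and from about 3.75 years. A programmer who applies the table as written would leave early-withdrawal scans on days 2-638 and 822-1369 out of the by-visit analysis, although they were obtained for a named endpoint. Inclusion would then depend on when a subject left the trial.

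There is also a mismatch at Month 24. Appendix H lets a scan up to 6 months earlier, from about day 548, stand in for the Month 24 scan. The SAP window opens at day 639. A scan on days 548-638 can therefore excuse the subject from the Month 24 scan and yet not count as one.

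**Working it through.** **Windows.** Midpoints recomputed from the nominal days in Table 9.a:
- Months 18 and 24: (548 + 731)/2 = 639.5
- Months 24 and 30: (731 + 913)/2 = 822
- Months 24 and 66: (731 + 2009)/2 = 1370

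The Month 24 bounds are thus midpoints with clinic visits at which no vMRI is scheduled. The Final bound equals the midpoint of the two scheduled follow-up vMRI visits. The stretch between them, days 822-1369, is left uncovered, as are days 2-638.

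**Dropout model.** SAP section 8.0 assumes an "annual dropout rate of 12% (or cumulative dropout rate of 47% over 5 years". With retention S(d) = 0.88^(d/365.25), the 5-year figure is 1 - 0.88^5 = 47.2%, which reproduces the plan's 47%.

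**Who would have a scan in a gap.** Footnote (b) requires no scan within 6 months (about 183 days) of the last one. The relevant withdrawals therefore start at about day 183 after the baseline scan, and at about day 731 + 183 = 914 after a Month 24 scan.
- First gap, days 183-638: S(183) - S(638) = 0.938 - 0.800 = 13.8%, about 41 of 300.
- Second gap, days 914-1369: S(914) - S(1369) = 0.726 - 0.619 = 10.7%, about 32 of 300.
- Total: 24.5%, about 73 of 300.

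**Sensitivity.**
- With the baseline scan as early as day -35 and the Month 24 scan within its 2-week window either side, the total is about 24-26%.
- With MCI/AD events as a competing exit (15% and 9% over 5 years, 5:4 allocation), dropout in the gaps is about 23%.
- With incomplete attendance for the early-withdrawal scan (rates assumed; the documents give none): at 80%, 0.80 × 24.5% = 19.6% (about 59 subjects); at 50%, 0.50 × 24.5% = 12.2% (about 37).

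**What is lost.** A first-gap subject normally has no other follow-up scan and would leave the analysis altogether. A second-gap subject would normally already have a Month 24 scan and would lose only the later value.

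**The case against.** The strongest reply is that these scans may not be meant to pass through the windows at all. The vMRI models are described as similar to the NPI-Q model, and SAP 9.9.9 runs that model from baseline to EoS/EW. Elsewhere the SAP names EoS/EW separately from the visits. On that reading an early-withdrawal scan is analysed as EoS/EW whatever its day. This is plausible, so a reader who infers that the scans will certainly be discarded goes further than the documents allow. It does not settle the matter, however. The vMRI sentence specifies analysis by study visit without naming EoS/EW, and Table 9.a puts an explicit day limit on the vMRI Final row. Two programmers could properly build different datasets.

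A second reply is that the midpoint rule is not broken. It is qualified as general, it refers to study visits rather than vMRI visits, the SAP claims exhaustive windows only for safety variables, and a narrow window keeps a 2-year change near 2 years. This stands as far as it goes: a rule violation should not be alleged. It does not explain where the other scans belong.

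Third, the sub-study is stated not to be designed or powered for quantitative change (Protocol Appendix H; SAP section 8.0). That stands, and it limits the importance of the point.

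**Conclusion.** The two gaps and the Month 24 mismatch are on the face of the documents. Up to about a quarter of sub-study subjects (24.5%, about 73 of 300) could have an early-withdrawal scan with no vMRI window. For up to about 14% it would normally be the only follow-up scan.

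This rests on the trial-wide 12% annual dropout holding in the sub-study, and on every withdrawing subject having the scan that the 6-month rule requires. It is a ceiling. Protocol 7.5 asks only for efforts to complete early-withdrawal procedures, and SAP 9.1.3 excludes efficacy data obtained more than 7 days after the last dose in any case. About 12-20% follows from an assumed 50-80% attendance.

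Two stronger inferences are not supported:
- A reader might count every withdrawal on the uncovered days: 20.0% + 13.1% = 33.1%, or 13.8% + 13.1% = 26.9% after removing only the first 6 months. Footnote (b) requires no scan for some of those subjects, and it applies after the Month 24 scan as well as after baseline.
- A reader might suppose that early leavers have the most atrophy, so that the result would be biased in a known direction. Nothing in the documents shows this. What can be said is that inclusion would depend on the time of leaving.

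This is a minor point. The primary and key secondary analyses are untouched.

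**What to change.** Amend SAP 9.1.3, Table 9.a, before unblinding:
1. State that any EoS/EW vMRI scan is assigned to the EoS/EW analysis visit regardless of study day. This leaves no such scan without a visit.
2. Open the Month 24 vMRI window at about day 548 (731 - 183), so that a scan Appendix H accepts in place of the Month 24 scan counts as Month 24.
3. Add a precedence rule for an early-withdrawal scan that falls inside the Month 24 window, saying which visit it serves or whether it serves both.
4. Name EoS/EW explicitly in the vMRI paragraph of SAP 9.9.9.

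The cost is two table entries and a few sentences, with no new scans. The small downside is that EoS/EW scans would span varied follow-up, and some Month 24 values would come from nearer 18 months, so the distribution of scan times should be reported by arm. Adjustment for time since baseline is optional and best kept as a sensitivity analysis, because time of leaving is a post-randomisation variable that treatment may affect.
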